#### 9.3.1 Hematologic Toxicity

**At the start of each cycle if the patient is receiving carboplatin, the ANC must be  $\geq 1000/\text{mm}^3$  and the platelet count must be  $\geq 80,000/\text{mm}^3$ .** Platelets must be  $\geq 100,000$  for study entry. Growth factors may be used in accordance with American Society of Clinical Oncology (ASCO) and National Comprehensive Cancer Network (NCCN) guidelines (Smith et al. 2006; NCCN 2012). Upon recovery, dose adjustments at the start of a subsequent cycle will be made on the basis of the lowest platelet and neutrophil values from the previous cycle (see Table below).

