##### 9.3.1.1 Carboplatin Dose Modification for Hematologic Toxicities

Toxicity	Carboplatin Dose
ANC $< 500/\text{mm}^3$ and platelets $\geq 50,000/\text{mm}^3$	Decrease AUC by 1
Platelets $< 50,000/\text{mm}^3$ , regardless of ANC	Decrease AUC by 1
Platelets $< 50,000/\text{mm}^3$ with Grade $\geq 2$ bleeding, regardless of ANC	Decrease AUC by 2
ANC $< 1000/\text{mm}^3$ plus fever of $\geq 38.5^\circ\text{C}$	Decrease AUC by 1

All dose reductions for the first episode of neutropenic fever or thrombocytopenia (platelet count  $< 25,000$  or  $< 50,000$  with bleeding or that requires transfusion) are permanent. If a second episode of neutropenic fever or thrombocytopenia requiring dose reduction occurs, the dose of carboplatin will be reduced according to physician judgment and local standard practice. Colony-stimulating factors, such as granulocyte colony-stimulating factor, may be used instead of dose reduction for neutropenic fever or Grade 4 neutropenia, according to the local standard practice and ASCO guideline. Patients who require a third dose reduction will immediately discontinue chemotherapy.

In the event that dose adjustments are needed for both ANC and platelets, patients are to receive the lower dose.

**For Grade 3 ANC toxicity** (ANC  $< 1000-500/\text{ml}$ ), carboplatin should be withheld until the patient recovers completely or to Grade 1 toxicity. The treatment should then be resumed at 50% dose (permanent dose reduction). If recovery to Grade 1 toxicity does not occur within 3 weeks, the patient's chemotherapy will be discontinued.

Treatment with carboplatin can be delayed for up to 3 weeks until the Day 1 ANC is  $\geq 1000/\text{mm}^3$  and the platelet count is  $\geq 80,000/\text{mm}^3$ . However, if the counts have not recovered in 3 weeks, the patient's chemotherapy will be dose-reduced, held until adequate neutrophil recovery, or

discontinued, according to physician judgment and local standard practice. If chemotherapy is held longer than 42 days, all study treatment should be discontinued.

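### Section 9.3.1.1 has two neutrophil dose rules for carboplatin, with no stated precedence and in inverted severity order: a permanent halving for ANC 500 to <1000, but one AUC unit off for ANC <500

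*Combined protocol and SAP*

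**What the plan says.** Both arms start carboplatin at AUC 6 every 21 days (section 8.1). Section 9.3.1 requires ANC ≥1000/mm³ and platelets ≥80,000/mm³ to start a cycle. After recovery, dose adjustments "will be made on the basis of the lowest platelet and neutrophil values from the previous cycle", by reference to the table in 9.3.1.1.

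That table has four rows. ANC <500/mm³ with platelets ≥50,000/mm³ reads "Decrease AUC by 1". The same step applies to platelets <50,000 whatever the ANC, and to ANC <1000 with fever of at least 38.5°C. Only platelets <50,000 with Grade ≥2 bleeding goes further: "Decrease AUC by 2". There is no row for afebrile ANC 500 to <1000.

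The text below the table adds three points:

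- "All dose reductions for the first episode of neutropenic fever or thrombocytopenia" are permanent. Nothing is said about permanence for afebrile ANC <500.
- Growth factor "may be used instead of dose reduction for neutropenic fever or Grade 4 neutropenia". Grade 3 is not named.
- The tie-break is "In the event that dose adjustments are needed for both ANC and platelets, patients are to receive the lower dose".

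A separate paragraph then covers Grade 3 ANC. Its range is printed per ml, while the rest of the section uses mm³. Carboplatin is withheld until full or Grade 1 recovery, and then: "The treatment should then be resumed at 50% dose (permanent dose reduction". Failure to reach Grade 1 within 3 weeks ends chemotherapy. The next paragraph deals with delays for ANC or platelets. At the same 3-week mark it lets the physician reduce, hold longer or stop, and all study treatment ends if the hold exceeds 42 days.

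**The concern.** Dose-reduction schedules normally cut more for worse toxicity. Here the milder neutrophil count carries the larger and expressly permanent cut, and the more severe one carries a smaller cut that growth factor can replace. Two sites could treat the same patient differently and each cite 9.3.1.1.

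The 3-week text decides whether carboplatin continues. In the control arm it is the only study drug, and under section 8.4 a control patient who stops it for toxicity cannot later cross over to atezolizumab unless the Protocol Chair makes an exception. The matter is therefore one of patient-level dosing and access to crossover.

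**Working it through.** Inputs: starting dose AUC 6 (8.1); the table and the Grade 3 paragraph (9.3.1.1); maximum dose = AUC × 150 mg (10.2). The Grade 3 range is read as per mm³. Dose is proportional to AUC, so half the dose is half the AUC at any renal function.

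From AUC 6, with no earlier reduction:

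| Event | Rule | New AUC | Cut | Dose at the 10.2 cap |
|---|---|---|---|---|
| None | – | 6 | – | 6 × 150 = 900 mg |
| ANC 500 to <1000 | 50% dose | 6 × 0.5 = 3 | 3/6 = 50% | 3 × 150 = 450 mg |
| ANC <500, platelets ≥50,000 | AUC minus 1 | 6 − 1 = 5 | 1/6 = 16.7% | 5 × 150 = 750 mg |
| Platelets <50,000 with Grade ≥2 bleeding | AUC minus 2 | 6 − 2 = 4 | 2/6 = 33.3% | 4 × 150 = 600 mg |

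The Grade 3 cut is 3 AUC units against 1 for the worse neutrophil count. It also exceeds the largest cut in the table.

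**After an earlier reduction.** The result depends on what the 50% refers to. From AUC 5, it is 5 × 0.5 = 2.5 (current dose) or 6 × 0.5 = 3 (starting dose), against 5 − 1 = 4, so the order is inverted either way. From AUC 4, it is 4 × 0.5 = 2 (current) against 4 − 1 = 3, inverted; or 6 × 0.5 = 3 (starting) against 3, equal. The only percentage convention in 9.3, footnote a of 9.3.2.1, uses the previous AUC. It belongs to the non-hematologic table.

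**Trigger.** The table works from the previous cycle's lowest counts. The Grade 3 paragraph does not say which count it uses.

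- If it is the nadir, every nadir of 500 to <1000 is halved and every nadir <500 loses one unit. The inversion covers all Grade 3 neutropenia.
- If it is the treatment-day count, a nadir of 500 to <1000 that recovers by Day 1 gets no cut and a nadir <500 loses one unit, which is the right order. On Day 1 itself, however, 500 to <1000 is halved and <500 still has only the one-unit rule. A nadir <500 with a Day 1 count of 700 meets both rules.

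**Fever.** The Grade 3 paragraph has no fever condition. A febrile patient with ANC 500 to <1000 therefore meets both the one-unit row and the halving. The tie-break applies when ANC and platelets both call for adjustment, so it does not settle two ANC rules.

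**Three weeks.** For Grade 3 ANC not recovered by then, one paragraph requires a stop and the next offers three choices. If the first is treated as a specific exception to the second, the milder count has the mandatory stop and ANC <500 has physician judgment.

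**The case against.** The best defence is that the two rules use different counts: the table the nadir, the Grade 3 paragraph the treatment-day value. Withholding until recovery is language for a patient due for treatment. This reading is plausible and would narrow the problem considerably, so a reader should not infer that every afebrile Grade 3 nadir is halved. But the section does not state it, and it leaves the Day 1 inversion in place.

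The 3-week paragraphs are not a strict contradiction. Stopping is among the options in the second, so stopping satisfies both. That stands, but the specific-versus-general reading is also unstated and puts the stricter outcome on the milder event.

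Other text softens the consequences. Section 9.4 lets the investigator reduce for a toxicity of any grade, so one AUC unit is not a ceiling for ANC <500, and it provides for departures to be approved in advance. Prophylactic pegfilgrastim (8.2.1) and guideline-based growth factor (9.3.1) are allowed. These provisions give discretion; none says which written rule applies.

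The crossover cost is also limited. Section 8.4 requires progression and inclusion-level laboratory values, and 5.1 sets ANC at ≥1000/mm³, so a patient who is still neutropenic could not cross over at that moment anyway. Later crossover is what is at stake.

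A reader might infer that the 50% rule must be a mistake because 10.2 lists maximum doses for AUC 6, 5 and 4 only. The documents do not support that. The table reaches AUC 3 too, since 6 − 2 − 1 = 3. That is only a second reduction, and the limit is "Patients who require a third dose reduction will immediately discontinue chemotherapy".

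**Conclusion.** The point holds. Section 9.3.1.1 has two neutrophil rules without precedence, in inverted severity order. From AUC 6 the cut is 50% for ANC 500 to <1000 against 16.7%, or none with growth factor, for ANC <500 with platelets ≥50,000. The scope depends on the unstated trigger: all Grade 3 neutropenia on a nadir reading, Day 1 counts only on a treatment-day reading. The inversion survives both. The 3-week text is an ambiguity that, on its most natural reconciliation, runs in the same wrong direction.

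The sizes assume the Grade 3 range is per mm³ and that no earlier reduction has been made. The documents do not show which rule the sponsor intended. A reader might infer that carboplatin exposure, and so the PFS comparison, is distorted. The documents give no rate of Grade 3 neutropenia and both arms follow the same carboplatin rules, so that is not supported. The defect should be corrected for consistent and safe dosing; it leaves the sample size and power untouched.

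**What to change.** Amend 9.3.1.1 so that one neutrophil rule applies:

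- Delete the Grade 3 paragraph's 50% cut and its separate mandatory 3-week stop.
- Add a table row for afebrile ANC 500 to <1000/mm³ with a cut no larger than AUC minus 1. No cut would also restore the order. If the row carries a cut, allow the same growth-factor substitution as for Grade 4.
- State that the table and the existing delay paragraph govern, with restart at Day 1 ANC ≥1000/mm³ and platelets ≥80,000/mm³.

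If the sponsor did intend 50% for Grade 3, keep it, make the ANC <500 and febrile rows at least as large, and apply the 3-week stop to them too. The 42-day limit can stay as it is.

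The cost is one wording amendment, approved by each institution's IRB under section 15.1. It adds no visits or procedures and leaves the statistical design unchanged.

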### 9.3.2 Non-Hematologic Toxicity

For Grade 3 or 4 non-hematologic toxicities, treatment should be delayed until resolution to less than or equal to the patient’s baseline value. Dose reductions at the start of the subsequent cycle will be made on the basis of non-hematologic toxicities from the dose administered in the preceding cycle. The table below provides the relevant dose adjustments for non-hematologic toxicities.

#### 9.3.2.1 Carboplatin Dose Modification on the Basis of Non-Hematologic

#### Toxicities in the Preceding Cycle

Toxicity	Adjusted Carboplatin Dose a
Diarrhea	Grade 3 or 4 b : 100% of dose
Oral mucositis	Grade 3 or 4: Decrease AUC by 1
Nausea/Vomiting	Grade 3 or 4: Decrease AUC by 1
Neurotoxicity (motor or sensory)	Grade 2: 100% of dose Grade 3 or 4: Decrease AUC by 1
Transaminase Elevation	Grade 3: Decrease AUC by 1 Grade 4: discontinue
Other	Grade 3 or 4: Decrease AUC by 1

AUC □ area under the concentration curve.

a If deemed appropriate by the treating physician, adjust carboplatin dose to the specified percentage of the previous AUC.

b Or any grade of diarrhea requiring hospitalization.

Nausea and/or vomiting should be controlled with adequate anti-emetics. If Grade 3 or 4 nausea/vomiting occurs in spite of anti-emetics, the dose should be reduced by 25% for the next course. If tolerated, the dose should be increased back to 100% as soon as possible.

If, on Day 1 of any treatment cycle, the patient has grade 2 oral mucositis, the treatment can be withheld until the oral mucositis is cleared. If the oral mucositis has not cleared in 3 weeks, the patient's chemotherapy will be discontinued. If acute Grade 3 oral mucositis occurs at any time, the dose should be given at a 75% dose when the oral mucositis is completely cleared. This is a permanent dose reduction.

### 9.3.3

## 9.4 Special Considerations

- For toxicities which are considered by the treating investigator unlikely to develop into serious or life-threatening events (e.g. alopecia, altered taste etc.), treatment may be continued at the same dose without reduction or interruption.
- The treating investigator may reduce a subject's dose for a toxicity of any grade/duration where s/he believes it to be in the best interests of the subject.
- Any consideration to modification of the above dose modification guidelines should be discussed with the Principal Investigator for approval or disapproval in advance.

## 10. DRUG FORMULATION/STORAGE/SUPPLY

### 10.1 Atezolizumab (MPDL3280A)

Atezolizumab is an investigational agent and will be supplied free-of-charge from Genentech.

#### 10.1.1 Formulation

The atezolizumab drug product is typically provided in a single-use 15 mL or 20 mL USP/Ph. Eur. Type 1 glass vial as a colorless-to-slightly-yellow, sterile, preservative-free clear liquid solution intended for IV administration. Other excipients of the atezolizumab drug product include histidine acetate, sucrose and polysorbate 20.

Atezolizumab must be refrigerated at 2°C – 8°C (36°F – 46°F) upon receipt until use. Atezolizumab vials should not be used beyond the expiration date provided by the manufacturer. No preservative is used in the atezolizumab drug product or the diluent; therefore, each vial is intended for single use only. Discard any unused portion of drug left in a vial. Vial contents should not be frozen or shaken and should be protected from direct sunlight. Once prepared, atezolizumab can be stored for up to 8 hours at room temperature.

For further details, see the atezolizumab Investigator’s Brochure.

#### 10.1.2 Dosage, Administration, and Storage

The dose level of atezolizumab to be tested in this study is 1200 mg (equivalent to an average body weight–based dose of 15 mg/kg) administered by IV infusion every 3 weeks (21 [± 2] days). Atezolizumab will be delivered in infusion bags with IV infusion lines that have product contacting surfaces of polyvinyl chloride (PVC) or polyolefin and 0.2 µm in-line filters (filter membrane of polyethersulfone [PES]). No incompatibilities have been observed between atezolizumab and PVC or polyolefin infusion materials (bags or infusion lines).

Administration of atezolizumab will be performed in a setting with emergency medical facilities and staff who are trained to monitor for and respond to medical emergencies.

The initial dose of atezolizumab will be delivered over 60 (± 15) minutes. If the first infusion is tolerated without infusion-associated AEs, the second infusion may be delivered over 30 (± 10) minutes. If the 30-minute infusion is well tolerated, all subsequent infusions may be delivered over 30 (± 10) minutes. For the first infusion, the patient’s vital signs (heart rate, respiratory rate, blood pressure, and temperature) should be determined within 60 minutes before, during (every 15 [± 5] minutes), and 30 (± 10) minutes after the infusion. For subsequent infusions, vital signs will be collected within 60 minutes before and within 30 minutes after the infusion. Vital signs should be collected during the infusion only if clinically indicated. Patients will be informed about the possibility of delayed post-infusion symptoms and instructed to contact their study physician if they develop such symptoms. **Atezolizumab should be administered prior to carboplatin.**

No premedication will be allowed for the first dose of atezolizumab. Premedication may be administered for Cycles  $\geq 2$  at the discretion of the treating physician. The management of infusion-related reactions (IRRs) will be according to severity as follows:

- In the event that a patient experiences a mild (NCI CTCAE Grade 1) IRR, the infusion rate should be reduced to half the rate being given at the time of event onset. Once the event has resolved, the investigator should wait for 30 minutes while delivering the infusion at the reduced rate. If tolerated, the infusion rate may then be increased to the original rate.
- In the event that a patient experiences a moderate IRR (NCI CTCAE Grade 2) or flushing, fever, or throat pain, the infusion should be immediately interrupted and the patient should receive aggressive symptomatic treatment. The infusion should be restarted only after the symptoms have adequately resolved to baseline grade. The infusion rate at restart should be half of the infusion rate that was in progress at the time of the onset of the IRR.
- For severe or life-threatening IRRs (NCI CTCAE Grade 3 or 4), the infusion should be stopped immediately, and aggressive resuscitation and supportive measures should be initiated. Patients experiencing severe or life-threatening IRRs will not receive further infusion and will be further managed as clinically indicated until the event resolves.

For anaphylaxis precautions, see the appendices.

Guidelines for dosage modification, treatment interruption, or discontinuation and the management of specific adverse events are provided in the protocol.

## 10.2 Carboplatin

Carboplatin is commercially available. Carboplatin should be administered intravenously according to local practice. **Carboplatin should be administered after atezolizumab if the patient is receiving atezolizumab.**

The carboplatin dose will be calculated using the Cockcroft and Gault formula.

For the purposes of this protocol, the GFR is considered to be equivalent to the creatinine clearance (CrCl). The CrCl is calculated by institutional guidelines or by the method of Cockcroft and Gault (1976) using the following formula:

$$\text{CrCl} = \frac{(140 - \text{age}) (\text{wt})}{72 \times \text{Scr}} \quad (\times 0.85 \text{ if female})$$

Where: CrCl = creatinine clearance in mL/min

age = patient's age in years

wt = patient's weight in kg

Scr = serum creatinine in mg/dL

If a patient's GFR is estimated on the basis of serum creatinine measurements by the isotope dilution mass spectroscopy method, the U.S. Food and Drug Administration (FDA) recommends that physicians consider capping the dose of carboplatin for desired

exposure (AUC) to avoid potential toxicity caused by overdosing.

The maximum dose is based on a GFR estimate that is capped at 125 mL/min for patients with normal renal function. No higher estimated GFR values should be used.

For a target AUC = 6, the maximum dose is  $6 \times 150 = 900$  mg.

For a target AUC = 5, the maximum dose is  $5 \times 150 = 750$  mg.

For a target AUC = 4, the maximum dose is  $4 \times 150 = 600$  mg.

See the FDA's communication regarding carboplatin dosing for more details at

<http://www.fda.gov/AboutFDA/CentersOffices/OfficeofMedicalProductsandTobacco/CDER/ucm228974.htm>

### **10.3 Drug Accountability**

Accountability for the drug at all study sites is the responsibility of the site Principal Investigator and designated Pharmacy representative. The investigator will ensure that the investigational drug is used only in accordance with this protocol. Drug accountability records indicating the drug's delivery date to the site, inventory at the site, use by each patient, and destruction locally will be maintained by the clinical site. Atezolizumab should be destroyed locally as per local policy. Accountability records will include dates, quantities, lot numbers, expiration dates, and patient numbers. These records should be sent to Genentech for filing.

exposure (AUC) to avoid potential toxicity caused by overdosing.

The maximum dose is based on a GFR estimate that is capped at 125 mL/min for patients with normal renal function. No higher estimated GFR values should be used.

For a target AUC = 6, the maximum dose is  $6 \times 150 = 900$  mg.

For a target AUC = 5, the maximum dose is  $5 \times 150 = 750$  mg.

For a target AUC = 4, the maximum dose is  $4 \times 150 = 600$  mg.

See the FDA's communication regarding carboplatin dosing for more details at

<http://www.fda.gov/AboutFDA/CentersOffices/OfficeofMedicalProductsandTobacco/CDER/ucm228974.htm>

### **10.3 Drug Accountability**

Accountability for the drug at all study sites is the responsibility of the site Principal Investigator and designated Pharmacy representative. The investigator will ensure that the investigational drug is used only in accordance with this protocol. Drug accountability records indicating the drug's delivery date to the site, inventory at the site, use by each patient, and destruction locally will be maintained by the clinical site. Atezolizumab should be destroyed locally as per local policy. Accountability records will include dates, quantities, lot numbers, expiration dates, and patient numbers. These records should be sent to Genentech for filing.

## 11. CORRELATIVE/SPECIAL STUDIES

### 11.1 Archived Tissue Samples

Metastatic tissue is the preferred sample; however, if the remaining tissue is insufficient to fit the requirements below, tissue from the patient's primary tumor is acceptable.

Formalin-fixed paraffin embedded tissue blocks from the patient's metastatic lesion collected for diagnostic and therapeutic purposes is requested for all patients enrolled in the study at the time of registration. They will be returned within 8 weeks (or earlier if requested); tissue taken from these blocks will not be returned.

In case the participating institutions are not allowed to release clinical paraffin embedded blocks from prior surgeries/biopsies, ideally we will need the following cut in this order:

#### **A. If sending prior metastatic biopsy (performed pre-enrollment for diagnostic purposes) then send:**

1. Six (6) 4  $\mu$ m unstained sections on charged slides (levels 1,6 for immune infiltrate assessment, levels 2-5 to Genentech for PDL-1 IHC)
2. Six (6) 10  $\mu$ m unstained sections on non-charged slides (Vanderbilt DNA/RNA isolation)
3. Twelve (12) 4  $\mu$ m unstained slides on charged slides (level 1 and 12 to be H&E stained upon receipt)

If remaining tissue is insufficient for the complete request, please send:

1. Six (6) 4  $\mu$ m unstained sections on charged slides (levels 1,6 for immune infiltrate assessment, levels 2-5 to Genentech for PDL-1 IHC)
2. Two 5 x 10  $\mu$ m peels in a DNase-free/RNase-free tube

If remaining tissue is very limited, please send:

- Six (6) 4  $\mu$ m unstained sections on charged slides (levels 1,6 for immune infiltrate assessment, levels 2,3,4,5 to Genentech for PDL-1 IHC)

#### **B. If sending primary tumor send:**

1. Six (6) 4  $\mu$ m unstained sections on charged slides (levels 1,6 for immune infiltrate assessment, levels 2-5 to Genentech for PDL-1 IHC)
2. Six (6) 10  $\mu$ m unstained sections on non-charged slides (Vanderbilt DNA/RNA isolation)
3. Two (2) 4  $\mu$ m unstained slides on charged slides (last will be H&E stained upon receipt)

If remaining tissue is insufficient for the complete request, please send:

1. Six (6) 4  $\mu$ m unstained sections on charged slides (levels 1,6 for immune infiltrate assessment, levels 2-5 to Genentech for PDL-1 IHC)

If remaining tissue is very limited, please send:

Six (6) 4 µm unstained sections on charged slides (levels 1,6 for immune infiltrate assessment, levels 2,3,4,5 to Genentech for PDL-1 IHC)

After removing all stray tissue from the area, the microtome blade and surrounding area should be wiped with 70% ETOH before starting to section the block and between patients to prevent contamination with extraneous tissue.

**All formalin-fixed paraffin embedded tissue and/or slides should be sent with a cold pack to avoid melting that could damage tissue analysis.**

Once a patient meets all other eligibility, and registers for the study, **collection of tissue from a metastatic site, if reasonably safe, is also a requirement for entry to this study. Pre-trial and post-progression biopsies should be collected.** Research tissue blocks prepared from these metastatic biopsies will not be returned. **All patients must have a biopsy of a metastatic site (if reasonably safe) at the end of treatment if the patient is removed for disease progression, or if on the carboplatin only arm and crossing over to atezolizumab.**

